4.4.1.1.1 Daily Intensity

Intensity will be categorized as follows: None, Grade 1, Grade 2, Grade 3, or Missing. The daily intensity will be recorded by the Investigator for solicited reactions whose scale is not a measure. For measurable solicited reactions, the intensity will be calculated at the time of the statistical analysis based upon the intensity scales defined in the protocol.

A reaction that is too large to measure (non-measurable [NM]) will be considered as Grade 3.

4.4.1.1.2 Maximum Overall Intensity

Maximum overall intensity is derived from the daily intensities and is calculated as the maximum of the daily intensities over the period considered. The maximum intensity during the solicited period will be computed without considering the ongoing period.

Note: The maximum overall intensity should be considered as "Missing" only if all daily intensities over the period considered are "Missing."

4.4.1.1.3 Presence

Presence of solicited reactions will be computed based on daily records during the solicited period. For any specific period, a subject would be considered to have a reaction if the intensity is greater than or equal to Grade 1 for at least one day during that period. If no data is recorded and the presence recorded by the Investigator is different from "No", the presence will be considered as "Missing."

4.4.1.1.4 Time of Onset

Time to onset is derived from the daily intensities. It corresponds to the first day with intensity of Grade 1, Grade 2, or Grade 3.

Note: If a reaction is not continuous (i.e., reaction occurs over two separate periods of time intervened by at least one daily intensity "Missing" or "None") then the time to onset is the first day of the first occurrence.

Time to onset will be displayed by period as follows:

Table 4.4: Categories for Time to Onset

Period of Time to Onset	
Injection Site Reactions (D0-D7)	Systemic Reactions (D0-D14)
D0 - D3	D0 - D3
D4 - D7	D4 - D7
	D8 - D14

4.4.1.1.5 Number of Days of Occurrence

The “number of days of occurrence” of a solicited reaction during the solicited period is computed as the number of days the solicited reaction is present, (intensity different from none or missing between D0 and the end of the solicited period), over the daily record period. For instance, for calculating number of days of fever occurrence, only daily temperature $\geq 38^{\circ}\text{C}$ will be considered.

Number of days of occurrence during and after the solicited period will be displayed by category (range) as follows:

Table 4.5: Categories for Number of Days of Occurrence

	Period of Number of Days of Occurrence	
	Injection Site Reactions	Systemic Reactions
During solicited period	1 - 3 days 4 - 7 days 8 days	1 - 3 days 4 - 7 days 8 - 14 days 15 days

4.4.1.1.6 Overall Number of Days of Occurrence

If a reaction is ongoing at the end of the solicited period, then the overall number of days of occurrence is derived from the daily intensities and the stop date of the reaction after the end of the solicited period. The overall number of days of occurrence is:

- $(\text{stop date} - \text{last vaccination date}) + (\text{number of days of occurrence within the solicited period}) - \text{length of the solicited period} + 1$

If the stop date is missing or incomplete (contains missing data [MD]), the overall number of days of occurrence will be considered as "Missing."

Table 4.6: Categories for Overall Number of Days of Occurrence

	Period of Overall Number of Days of Occurrence	
	Injection Site Reactions	Systemic Reactions
Ongoing period after D7 for injection site/D14 for systemic reactions	1 - 3 days 4 - 7 days ≥ 8 days Missing	1 - 3 days 4 - 7 days 8 - 14 days ≥ 15 days Missing

4.4.1.1.7 Ongoing

Ongoing is derived from the last daily intensity of the solicited period and the maximum intensity of the ongoing period.

If the last daily intensity of the solicited period is Grade 1, Grade 2, or Grade 3 and maximum intensity of the ongoing period is also Grade 1, Grade 2, or Grade 3, then the reaction is considered ongoing. In any other case, the reaction will not be considered as ongoing.

4.4.1.2 Unsolicited Non-serious AEs

4.4.1.2.1 Intensity

Intensity will be categorized as follows: None, Grade 1, Grade 2, Grade 3, or Missing. For unsolicited non-serious adverse events (AEs) the intensity will be recorded by the Investigator for AEs whose scale is not a measure. For measurable AEs that have the same preferred term (PT) as a solicited reaction, the intensity will be calculated at the time of the statistical analysis.

4.4.1.2.2 Last Vaccination

Last vaccination before an unsolicited non-serious AE is derived from the visit numbers provided in the clinical database and is calculated as follows:

- If an unsolicited non-serious AE has a non-missing visit number, the visit number should be used to determine the last vaccination before the unsolicited non-serious AE
- If the visit number is missing, then the start date should be used to determine the last vaccination before the unsolicited non-serious AE

4.4.1.2.3 Time of Onset

Time to onset in days following the vaccination will be computed as follows:

- Time to onset = start date – date of previous vaccination

If the start date of the AE is the same as the last vaccination date, then the onset is “0”.

If one of the dates is partially missing, time to onset will be considered as “Missing”. Events that occur before vaccination (negative time to onset) will not be included in the analyses but will be listed separately. The unsolicited non-serious AEs will be analyzed within 28 days after vaccination, which corresponds to AEs with a time to onset between 0 and 28 days after vaccination or missing. An AE with missing time to onset will be considered to have occurred just after the vaccination indicated by the visit number, so will be included in these tables.

Time to onset will be displayed by period as follows:

- D0-D3
- D4-D7
- D8-D14

- $\geq D15$
- Missing

4.4.1.2.4 Duration

The duration will be computed as: Duration = stop date of event - start date of event + 1.

If start or stop dates are unfilled (“blank”) or missing (contain “MD”) or ongoing is ticked, then the duration will be considered as “Missing.”

If the start date of the AE is the same as the last vaccination date, then the duration is 1 day.

Duration will be displayed by period as following:

- 1-3 days
- 4-7 days
- 8-14 days
- 15 days or more
- Missing

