4.4.1.3.3 Duration

Duration will be computed using the same methodology as for unsolicited non-serious AEs described in Section 4.4.1.2.4.

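### SAP 4.4.1.2.4 fixes the duration of vaccination-day unsolicited AEs and SAEs at 1 day, contradicting its own formula whenever the event ends after that day

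*SAP*

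**What the plan says.** SAP 4.4.1.2.4 gives three rules for the duration of unsolicited non-serious AEs.

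- The formula: "The duration will be computed as: Duration = stop date of event - start date of event + 1".
- The missing-data rule: if the start or stop date is blank or recorded as missing, "or ongoing is ticked, then the duration will be considered as" Missing.
- The vaccination-day rule: "If the start date of the AE is the same as the last vaccination date, then the duration is 1 day". It sets no condition on the stop date.

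The result is tabulated in five rows: 1–3, 4–7, 8–14, 15 days or more, and Missing. For SAEs, SAP 4.4.1.3.3 says: "Duration will be computed using the same methodology as for unsolicited non-serious AEs described in Section 4.4.1.2.4".

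The preceding section, SAP 4.4.1.2.3, has a near-identical sentence about onset: "If the start date of the AE is the same as the last vaccination date, then the onset is" zero. It also keeps "AEs with a time to onset between 0 and 28 days after vaccination or missing" in the analysis, so Day 0 onsets are tabulated. SAP 5.3.1.5 leaves missing or partial AE stop dates as missing, without imputation.

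**The concern.** The gap between vaccination and the start of an event determines time to onset. It says nothing about when the event ended. The onset sentence in 4.4.1.2.3 therefore follows from the onset formula, but the parallel duration sentence does not follow from the duration formula, in which the vaccination date does not appear.

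The protocol lists duration among the possible descriptors of the safety endpoints (9.2.2.2), and the SAP commits to tabulating it. The events exposed to the rule are those closest to injection. They include every immediate unsolicited systemic AE, since these occur within 30 minutes of vaccination (protocol 9.2.2.3.1). If the rule is programmed as written, long-lasting Day 0 events will be shown as short ones.

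**Working it through.** **Inputs.** All rules come from SAP 4.4.1.2.4: the formula "Duration = stop date of event - start date of event + 1", the fixed value of 1 day when the start date equals the last vaccination date, and the display rows. The documents give no event data, so the stop days below are illustrative.

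**Step 1: known stop date.** Count days from vaccination and set onset at Day 0. The formula then gives stop day − 0 + 1.

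| Stop day | Formula (days) | Row by formula | Vaccination-day rule (days) | Row by that rule |
|---|---|---|---|---|
| D0 | 0 − 0 + 1 = 1 | 1–3 | 1 | 1–3 |
| D1 | 1 − 0 + 1 = 2 | 1–3 | 1 | 1–3 |
| D2 | 2 − 0 + 1 = 3 | 1–3 | 1 | 1–3 |
| D3 | 3 − 0 + 1 = 4 | 4–7 | 1 | 1–3 |
| D6 | 6 − 0 + 1 = 7 | 4–7 | 1 | 1–3 |
| D9 | 9 − 0 + 1 = 10 | 8–14 | 1 | 1–3 |
| D13 | 13 − 0 + 1 = 14 | 8–14 | 1 | 1–3 |
| D14 | 14 − 0 + 1 = 15 | 15 or more | 1 | 1–3 |
| D20 | 20 − 0 + 1 = 21 | 15 or more | 1 | 1–3 |
| D27 | 27 − 0 + 1 = 28 | 15 or more | 1 | 1–3 |

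The SAP's 1-day value is reproduced by its formula only for a D0 stop. For D1 and D2 stops the value is wrong but the row is right. From D3 onward both are wrong.

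**Step 2: direction.** A stop date cannot precede the start date, so the formula never gives less than 1 day. With a known stop date, the vaccination-day rule can therefore shorten a duration or leave it unchanged, but never lengthen it. An event of the same length that starts on Day 1 is classified correctly.

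**Step 3: ongoing event or no stop date.** A Day 0 event of this kind meets two rules in the same section: one returns Missing, the other 1 day. The SAP does not say which applies first. Section 5.3.1.5 (no imputation of stop dates) and the statement in 5.3.1 that no replacement is done both sit better with Missing, but neither mentions the vaccination-day sentence.

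**Step 4: scope.** The rule reaches unsolicited non-serious AEs directly and SAEs by cross-reference. Solicited reactions have their own derivations from daily records (SAP 4.4.1.1.5 and 4.4.1.1.6) and are outside it.

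**The case against.** The best defence is that this is a drafting slip with limited consequences. The sentence may be a copy of the onset sentence, or the vaccination date may have been written where the event's stop date was meant. The documents do not say, so this is inference. Safety is descriptive with no hypotheses tested, and start and stop dates are collected, with the stop dates of related AEs actively sought (protocol 9.2.2.3.3). SAE outcome is also tabulated and listed (SAP 4.4.1.4.3), so an unresolved Day 0 SAE would remain visible there. All of this stands and limits the weight of the point. It does not remove the contradiction: no other section withdraws or qualifies the sentence for an event with a known later stop date.

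A reader might infer more than the documents support:

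- *That every Day 0 event is misreported.* Events that end on Day 0 are correct, and those that end on Day 1 or Day 2 stay in the right row.
- *That ongoing Day 0 events will be shown as lasting 1 day.* They also meet the Missing rule. What is established is an unstated order of rules.
- *That a definite share of AEs is misplaced.* The documents give no count of Day 0 onsets or of how long they lasted, so no share can be derived.
- *That the information is lost.* Only the derived duration and its tables are affected; the dates remain in the database.

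**Conclusion.** The point holds as an internal contradiction in the derivation. Followed literally, SAP 4.4.1.2.4 gives a wrong duration for any unsolicited AE or SAE that starts on the vaccination day and ends later. It puts the event in the wrong row when the true duration is 4 days or more. For known stop dates the error runs only towards shorter durations. For ongoing events or missing stop dates, the defect is an unstated precedence between two rules.

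The conclusion assumes that the sentence is programmed as written. How many events would change row cannot be estimated from the documents. The non-inferiority tests, other immunogenicity analyses and solicited-reaction tables are unaffected. The sentence should be corrected before the safety tables are relied on; it does not threaten the trial's main conclusions.

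**What to change.** In SAP 4.4.1.2.4, delete the vaccination-day sentence. Alternatively, change its condition so that the start date is compared with the stop date of the event; the sentence then merely restates the formula, since equal dates give 0 + 1 = 1 day.

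Either way, state that stop date minus start date plus 1 applies to all unsolicited AEs and SAEs, and that the Missing/ongoing rule takes precedence. Section 4.4.1.3.3 picks up the correction through its cross-reference.

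The cost is a small text edit and one programming condition, with no new data. If the programs already use the formula alone, only the SAP text needs to be brought into line.

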4.4.1.3 SAEs

4.4.1.3.1 Last Vaccination

Last vaccination will be computed using the same methodology as for unsolicited non-serious AEs described in Section 4.4.1.2.2.

4.4.1.3.2 Time of Onset

Time to onset will be computed using the same methodology as for unsolicited non-serious AEs described in Section 4.4.1.2.3.

SAEs will be analyzed throughout the study using the following periods:

- Within 28 days after each/any injection
- During the study (i.e., all SAEs occurred during the study)

An SAE with missing time of onset will be considered to have occurred after the vaccination indicated by the visit number, so will be included in these tables.

Note: SAEs that occurred before vaccination (negative time to onset) will not be included in analysis, but will be listed separately.

Note for SAEs: Elapsed time from last vaccination recorded will be calculated if the SAE occurred within 24 hours of vaccination.

4.4.1.3.3 Duration

Duration will be computed using the same methodology as for unsolicited non-serious AEs described in Section 4.4.1.2.4.

4.4.1.4 Other Safety Endpoints

4.4.1.4.1 Action Taken

This information will be presented for solicited reactions after each injection. Listing will be also presented separately. No derivation or imputation will be done.

4.4.1.4.2 Seriousness

This information will be presented for all and related SAE within 28 days post-injection and throughout the study. Listing will be also presented separately. No derivation or imputation will be done.

4.4.1.4.3 Outcome

This information will be presented for all and related SAE within 28 days post-injection and throughout the study.. Listing will be also presented separately. No derivation or imputation will be done.

4.4.1.4.4 Causality

This information will be summarized as collected. Missing causality (relationship) will be handled as described in Section 5.3.1.2.

4.4.1.4.5 AEs Leading to Study Discontinuation

A flag is available in the clinical database for all AEs in order to identify AEs leading to discontinuation.

4.4.1.4.6 AEs of Special Interest (AESIs)

The following serious AESIs (reported as SAEs) will be considered:

- Serious hypersensitivity/allergic reactions occurring in all subjects within 7 days after vaccination
- Serious viscerotropic disease occurring in all subjects within 30 days after vaccination
- Serious neurotropic disease occurring in all subjects within 30 days after vaccination

- Serious dengue disease requiring hospitalization¹ occurring in all subjects at any time during the study

The following non-serious AESI will be considered:

Hypersensitivity/allergic reactions occurring in all subjects within 7 days after vaccination

4.4.2 Immunogenicity

4.4.2.1 Computed Values for Analysis

For the computation of GMT/GMCs, any titer/concentration reported as < the lower limit of quantification (LLOQ) will be converted to a value of $\frac{1}{2}$ LLOQ.

While a single approach was used for GMT/GMCs, two different approaches for geometric mean of the titer ratios [GMTR]/geometric mean of concentration [GMCR] will be applied:

- For CYD dengue vaccine, < LLOQ will be converted to $\frac{1}{2}$ LLOQ for a numerator and < LLOQ will be converted to LLOQ for a denominator
- For Tdap Vaccine, < LLOQ will be converted to $\frac{1}{2}$ LLOQ for a numerator and < LLOQ will be converted to LLOQ for a denominator when only one of either the numerator or denominator is < LLOQ. If both the numerator and denominator are < LLOQ, then both will be converted in the same way.

4.4.2.2 CYD Dengue vaccine Seropositivity and other Thresholds

Several thresholds of interest will be used to evaluate the immunogenicity of CYD Dengue vaccine.

For each threshold applied on each serotype, the derived indicator will be "Yes" for that serotype if the computed value meets the threshold, otherwise indicator will be "No".

At baseline and 28 days after the 1st dose of CYD Dengue vaccine*, the thresholds considered are:

- Seropositivity: titer ≥ 10 (1/dil)
- Distribution rates of titers against each serotype according to the following predefined thresholds (1/dil): $<10, \geq 10, \geq 20, \geq 30, \geq 40, \geq 60, \geq 80, \geq 100, \geq 120, \geq 140, \geq 160, \geq 180, \geq 200, \geq 220, \geq 240, \geq 260, \geq 280, \geq 300, \geq 320, \geq 340, \geq 360, \geq 400, \geq 640$ and ≥ 1280

* Objectives on the 3rd dose are not applicable due to the early termination of study (cf. section 5.7)

¹ A hospitalized subject is any subject admitted to hospital with bed attribution or any healthcare institution and requiring in-patient care.

4.4.2.3 CYD Dengue vaccine Seropositivity against at least X serotype(s)

The criteria below will be computed for each subject and visit as soon as at least one of the four dengue serotype result is different from missing or not-reportable ("NR") (i.e. coded no result in the serology database):

- Number and percentage of subjects with antibody (Ab) titer ≥ 10 (1/dil) against at least 1, 2, 3, or the 4 serotypes with the parental dengue virus strains.

Titer(s) ≥ 10 (1/dil) for at least X serotype(s) with parental dengue virus strains is computed as a Yes/No/Missing variable (note: in the case no titer is available the variable will be missing). If at least X among the 4 serotypes titers meet the threshold then the variable is derived to "Yes", otherwise if at least one titer is available and does not meet the threshold the variable is derived to "No". For the percentage calculation, all the subjects with at least one titer available regardless of the serotype will be considered in the denominator.

4.4.2.4 Tdap Seroprotection

For each antigen, the derived indicator will be "Yes" for that test if the computed value meets the seroprotection threshold, otherwise indicator will be "No".

At baseline and 28 days after the dose of Tdap vaccine, the thresholds considered are:

- anti-D Ab concentrations ≥ 0.1 IU/mL
- anti-T Ab concentrations ≥ 0.1 IU/mL

4.4.2.5 Tdap Booster response

The booster response against pertussis components (PT, FHA, PRN and FIM2+3) will be calculated based on Ab concentration rises between pre (D0) and post-vaccination (28 days after the dose of Tdap vaccine). The booster response is defined as:

- A post-vaccination Ab concentration $\geq 4 \times$ LLOQ when pre-vaccination concentration is $<$ LLOQ
- A post-vaccination Ab concentration $\geq 4 \times$ pre-vaccination Ab concentration when pre-vaccination concentration is \geq LLOQ but $< 4 \times$ LLOQ
- A post-vaccination Ab concentration $\geq 2 \times$ pre-vaccination Ab concentration when pre-vaccination concentration is $\geq 4 \times$ LLOQ

For each pertussis components (PT, FHA, PRN and FIM2+3), the derived indicator will be "Yes" for that test if the computed value meets the booster response definition, otherwise indicator will be "No".

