### 5.1.4 Visit Procedures

#### Visit 1 (Day 0): Inclusion, Randomization, and Vaccination

The Investigator or designated study personnel will:

- 1) Give the subject's parent/legally acceptable representative information about the trial, obtain written informed consent (ICF and AF when applicable), and give him/her a signed copy.
- 2) Obtain significant medical history about the subject and history of dengue infection/vaccination.
- 3) Collect demographic data.
- 4) Check concomitant medications and record every reportable medication ongoing at the time of vaccination.
- 5) Check inclusion and exclusion criteria for eligibility.
- 6) Allocate a subject number to the subject.
- 7) Scratch-off the randomization list to obtain the group allocation, and sign it.
- 8) Perform a physical examination
- 9) Record the subject's axillary temperature (Group 2).
- 10) For female subjects of childbearing potentiala, perform a urine pregnancy test (Group 2).

a To be considered of non-childbearing potential, a female must be pre-menarche or post-menopausal for at least 1 year, surgically sterile, or using an effective method of contraception or abstinence from at least 4 weeks prior to vaccination and until at least 4 weeks after vaccination.

- 11) Obtain blood samplea from subjects in Group 2 (see [Section 7.1](#) for detailed instructions regarding the handling of blood samples). Blood is to be taken from the limb opposite to the one that will be used for vaccination.
- 12) Review temporary and definitive contraindications to vaccination.
- 13) Inject Tdap vaccine to subjects from Group 2.
- 14) Keep the subject from Group 2 under observation for 30 minutes, and record any immediate AE in the source document (Group 2).
- 15) Record the date of injection, the site and side of injection and the route of administration, as well as the dose number of the vaccine (Group 2).
- 16) Give the subject or parent/legally acceptable representative of subjects in Group 2 a diary card (DC), a thermometer, and a ruler, and go over the instructions for their use. Subjects from Group 1, who will not be vaccinated at V01, will receive a DC for the collection of SAE only.
- 17) Remind the subject or parent/legally acceptable representative to bring back the DC when they return for Visit 2 at a specified date and time.
- 18) Remind the subject or parent/legally acceptable representative to notify the site in case of an SAE.

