**Table 7.1: Blood sampling volume (mL) per visit**

| Visit Number
Trial Timelines (Days/Months) | V01
D0                          | V02
M1 (D0+28D)                 | V03
M2 (M1+28D)                 | V07
M14 (M13+28D)               |
|---|------------------------------------|------------------------------------|------------------------------------|------------------------------------|
| Time Windows (Days)                           |                                    | +14                                | +14                                | +14                                |
| Dengue Neutralizing Abs                       |                                    | 4 (Group 1)
4 (Group 2)         | 4 (Group 1)
4 (Group 2)         | 4 (Group 1)
4 (Group 2)         |
| T, D, PT, FHA, PRN, and FIM2+3 Abs            | 0 (Group 1)
2 (Group 2)         | 2 (Group 1)
2 (Group 2)         | 2 (Group 1)
0 (Group 2)         | -                                  |
| TOTAL (mL)                             | 0 (Group 1)
2 (Group 2) | 6 (Group 1)
6 (Group 2) | 6 (Group 1)
4 (Group 2) | 4 (Group 1)
4 (Group 2) |

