##### *Tdap Immunogenicity:*

- Ab concentrations against PT, FHA, PRN, and FIM2+3, as measured by ELISA, at baseline (D0 for group 2, M1 for Group 1) and 28 days after the dose of Tdap vaccine
- Anti-T and anti-D Ab concentrations  $\geq 0.1$  IU/mL, as measured by ELISA for T and by MIT-TNA for D, at baseline (D0 for group 2, M1 for Group 1) and 28 days after the dose of Tdap vaccine

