3.1 Trial Design

This is a Phase IIIb, randomized, open label, multicenter study in 688 healthy subjects aged 9 to 60 years in the Philippines.

Subjects were to receive the CYD dengue vaccine according to a 3-dose schedule, given 6 months apart. A booster dose of Tdap vaccine (Adacel®) was to be administered either concomitantly to or before (sequential administration) the first dose of CYD dengue vaccine.

Subjects were to be randomized according to a 1:1 ratio into one of the 2 following groups with stratification on age (9 to 11 years, 12 to 17 years, 18 to 45 years and 46 to 60 years):

- **Group 1:** subjects were to be administered the first dose of CYD dengue vaccine concomitantly with the booster dose of Tdap vaccine at the second visit (V02; M1)
- **Group 2:** subjects were to receive Tdap vaccine at the first visit (V01; D0), and then CYD dengue vaccine 28 days later at the second visit (V02; M1)

The stratification was to be considered in order to balance the potential difference in terms of booster response by age group for the pertussis antigens (PT, FHA, PRN and FIM2+3).

Since the CYD dengue is to be administered according to a 3-dose schedule, given 6 months apart, initial trial design included administration of the second and third doses of CYD dengue vaccine at V04 (Month 7 [M7] and at V06 (M13) in all subjects.

At the time of study hold linked to the recommendation from IDMC not to vaccinate seronegative individuals anymore based on the results of the exploratory case-cohort study, all but 19 subjects (from both, Group 1 and Group 2) did receive dose 2 of the CYD dengue vaccine as planned. Following the IDMC recommendations, Sanofi Pasteur paused all vaccinations in CYD66 study, determined baseline serostatus and the Principal Investigators have communicated serostatus information to subjects already included in the study. In addition, the study protocol was amended to reflect the IDMC recommendations. The Sponsor has not received any feedback nor approval for the protocol amendment from Philippines FDA and has therefore decided to put an end to the CYD66 study with a last visit (which served as termination visit) of the subjects in order to inform them of the end of the study and to perform the last safety follow up. As a consequence, no more CYD dengue vaccine were administered to any subjects included in the study since the study hold. More details will be mentioned in the CSR

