3.2 Trial Plan

A schedule of assessments and study vaccinations was provided in the table of study procedures (Table 3.1).

All information collected during the study visits should be reported into the source documents. Some of the following information was to be recorded in the electronic case report form (eCRF).

Table 3.1: Study procedures as per initial study protocol

Phase IIIb Trial, 4 Vaccinations, 7 Visits and 3 or 4 Blood Samples (depending on group allocation), 19 Months Duration Per Subject. One Safety Follow-up Phone Call (PC) will be given 6 months after the last injection and 3 Interim phone calls will be given during the 6-month period after each CYD dengue vaccine injection (approximately 3 months after vaccination). .

Visit Number (V)	V01	V02	V03	V04	V05	V06†††	V07†††	Phone call***†††††
Trial Timelines* (Days/Months)	D0	M1 (V01+28D)	M2 (V02+28D)	M7 (V04+28D)	M8 (V06+28D)	M13 (V06+28D)	M14 (V06+28D)	Last vaccination+6M
Time Windows (Days)	+14	+14	+14	+20	+14	+20	+14	+30
Assent or Informed Consent	X							
Inclusion/Exclusion Criteria	X	X (Group 1)						
Contraindication	X (Group 2)	X		X			X	
Significant Medical History	X							
History of Dengue Infection/Vaccination	X							
Temperature	X (Group 2)	X		X			X	
Physical Examination†	X	X	X	X	X	X	X	X
Urine Pregnancy Test‡	X (Group 2)	X		X			X	
Demography/Body Stature	X							
Randomization	X							
Blood Sampling (BL) for Immunogenicity††								
T, D, PT, FHA, PRN, and FIM2+3	BL (Group 2)	BL	BL (Group 1)				BL	
Dengue Serotypes 1, 2, 3, and 4		BL	BL					
Tdap Vaccination §	X (Group 2)	X (Group 1)						
CYD dengue Vaccination §		Dose 1		Dose 2		Dose 3		
Post-injection phone calls (PC)**								Interim phone calls will be given during the 6-month period after each CYD dengue vaccine injection. The last phone call will be held 6 months after the last injection.
30-Min. Observation Period	X (Group 2)	X (Group 2)		X				
Injection Site and Systemic Events Collected***				X	X	X	X	X

Visit Number (V)	V01	V02	V03	V04	V05	V06†††	V07†††	Phone call***†††
Diary Card (DC) DC Provided	X (Group 1 for SAE only, and Group 2)	X	X	X	X	X	X	
DC Collected		X		X		X	X	
Memory Aid (MA) MA Provided							X	
MA Checked							X	
Concomitant Therapy†‡	X	X	X	X	X	X	X	X
Telephone Contact								

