Blood Sampling (BL) for virological confirmation of hospitalized suspected dengue cases§§	All acute febrile illness with diagnosis of hospitalized suspected dengue case within the first 5 days after fever onset, anytime throughout the trial period							
SAEs and AESIs collected***								
Termination Record§§§							X	

AESI: AE of special interest; BL: blood sample; D: Day; M: Month; MA: Memory Aid; SAE: Serious adverse event; V: Visit

* Timelines must be calculated based on the date of vaccination, not the date of visit.

** Interim phone calls will be given during the 6-month period after each CYD dengue vaccine injection: 3 months after Visit 2 (PC1: M4 [M1 + 3 months]), 3 months after Visit 4 (PC2: M10 [M7 + 3 months], and 3 months after Visit 6 [PC3: M16 M13 + 3 months]). The last PC will be held 6 months after the last vaccination.

† Physical examination will be performed if necessary, based on the health status of the subject.

‡ For female subjects of childbearing potential (e.g., a female subject who has reached menarche).

§ CYD and Tdap will be administered in 2 different sites, with the CYD dengue vaccine administered in one deltoid and Tdap in the other deltoid

§§ Concomitant therapy and ongoing medication will be collected for Days 0–28 after each injection only

§§§ Blood samples planned during vaccination visits will be taken before vaccination

†† Solicited injection site reactions will be collected for Days 0–7 after each injection. Solicited systemic reactions will be collected for Days 0–14 after each injection. Unsolicited events will be collected for Days 0–28 after each injection.

††† In such case, 1 unplanned acute blood sample (approximately 3 mL) will be collected for virological confirmation of hospitalized suspected dengue case SAEs will be reported throughout the study and AESIs will be collected in defined time windows according to the type of AESI (hypersensitivity/allergic reactions [serious or not] within 7 days after each CYD dengue vaccine injection, serious viscerotropic within 30 days after each CYD dengue vaccine injection, serious dengue cases requiring hospitalization (hospitalized VCD case) will be reported during the entire study).

*** Termination form will be completed

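### Does the D0 label in SAP 4.4.2.5 leave Group 1 without a pre-Tdap value for the pertussis booster response?

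*SAP*

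**What the plan says.** SAP 4.4.2.5 covers the four pertussis antigens and states that the response for each antigen "will be calculated based on Ab concentration rises between pre (D0) and post-vaccination (28 days after the dose of Tdap vaccine". Three criteria follow, chosen by whether the pre-vaccination concentration is below the LLOQ, between one and four times the LLOQ, or higher. The indicator is Yes if the computed value meets the definition and No otherwise.

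SAP 3.1 fixes the visits. For Group 2, "subjects were to receive Tdap vaccine at the first visit (V01; D0"). Group 1 has its first CYD dose "concomitantly with the booster dose of Tdap vaccine at the second visit (V02; M1"). In SAP Table 3.1 the blood-sampling row for "T, D, PT, FHA, PRN, and FIM2+3" shows Group 2 only at V01, both groups at V02 and Group 1 only at V03. A footnote to that table adds: "Blood samples planned during vaccination visits will be taken before vaccination".

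The protocol agrees. The Visit 1 instructions in section 5.1.4 read "Obtain blood sample a from subjects in Group 2", and the Tdap-antibody volumes in mL at V01 in Table 7.1 are "0 (Group 1) 2 (Group 2"). Section 9.2.1.1 places the Tdap measurements "at baseline (D0 for group 2, M1 for Group 1) and 28 days after the dose of Tdap vaccine".

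**The concern.** Section 4.4 of the SAP holds the calculation methods, so it is the text a programmer would follow. In the schedule, D0 heads the V01 column. A program that takes the pre-value from the D0 visit for every subject finds none for Group 1, because no blood is drawn from that group at V01.

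The section gives no Missing level for the indicator. Two poor outcomes are then conceivable. If Group 1 is left blank, the table has one arm. If absent values fall through to No, Group 1 shows 0%. With equal planned arms and a Group 2 rate of r, the pooled rate would become (0 × 344 + r × 344)/688 = r/2. Either outcome would spoil the booster-response comparison between concomitant and sequential administration.

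The label is also the SAP's own addition. The booster definition in protocol 12.1.2.2 speaks only of concentrations before and after vaccination.

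**Working it through.** The documents give no figure to reproduce. The check is which sample can serve as the pre-Tdap value in each arm, and whether the text leads an analyst to it.

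**Samples with Tdap antibodies, by arm (SAP Table 3.1; protocol Table 7.1)**

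| | V01 (D0) | V02 (M1) | V03 (M2) |
|---|---|---|---|
| Group 1 | none (0 mL) | 2 mL, before Tdap | 2 mL, after Tdap |
| Group 2 | 2 mL, before Tdap | 2 mL, after Tdap | none (0 mL) |

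Each arm has one sample before Tdap and one after it. For Group 1 the only possible pair is V02 and V03. For Group 2 it is V01 and V02. The V02 draw in Group 1 precedes the injection, by the footnote to SAP Table 3.1. The literal reading names a sample that does not exist for Group 1, and only one sample can replace it.

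**What the rest of the text says**

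1. The three criteria in SAP 4.4.2.5 compare a pre-vaccination with a post-vaccination concentration. D0 appears only in the sentence that introduces them. That same sentence counts the post value from the Tdap dose, not from enrolment.
2. SAP 5.1.2.2 repeats the whole definition with no D0 label.
3. Protocol 9.2.1.1 and the synopsis blood-sampling text both give D0 for Group 2 and M1 for Group 1. SAP 4.2.1.1 refers the reader to 9.2.1.1. It cites protocol version 1.0, which was not available here; the mapping was read in the amended protocol.
4. SAP 4.4.1.1 uses D0 for the day of injection when it sets the solicited periods. On that usage the label would be right for both arms. Section 4.4.2.5 does not say that it adopts this meaning, so the point helps without settling the matter.

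**Whether absent values would be scored No**

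SAP 5.3.2 and protocol 12.3.2 rule out imputing missing immunogenicity values. Entering No for a subject with no pre-value amounts to assigning a result, so the r/2 outcome needs the analyst to set that rule aside. The Yes/otherwise-No form is also not peculiar to this derivation. SAP 4.4.2.2 and 4.4.2.4 use it too, applied to a computed value; only 4.4.2.3 spells out Missing.

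**What depends on the output**

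The pertussis comparison with a hypothesis is the GMC non-inferiority test in SAP 5.1.1.1, which uses post-vaccination concentrations only. The booster response is an additional descriptive summary in SAP 5.1.2.2 and is not among the Tdap endpoints listed in protocol 9.2.1.1. The powers in SAP Tables 5.2 to 5.5 and the 510-subject condition do not involve it.

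**The case for a change.** The strongest case for a change has two parts.

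The first is that a derivation should be programmable from its own text. The SAP shows that it can name visits by group, as it does for the post-Tdap sample in the PPT definition in 5.2.2. That is a fair criticism of the drafting, and the label is wrong for Group 1 as the schedule uses D0. It has no consequence when only one sample can be meant and the protocol says which.

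The second is the absent Missing level, which matters even with the right visit. Booster response is analysed on the FAS, which SAP 5.2.1 defines by receipt of at least one study vaccine dose, with no serology requirement. SAP section 1 reports 688 enrolled and 676 given CYD dose 1, so 688 − 676 = 12 did not reach that dose. A Group 2 subject among them may have had Tdap at V01 and no later sample, and would stay in the FAS. A Group 1 subject lost before V02 had no vaccine and would not. The documents do not split the 12 by arm. If all were in Group 2 they would be 12/344 = 3.5% of its planned size. The share could be greater in the non-immune rows, where SAP 4.4.5 would place a subject with no V02 titre. Samples that were not drawn or gave no valid result could add to this.

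What stands is that an explicit Missing level would be tidier. It is a general drafting point shared with two other derivations, and the no-imputation rule in 5.3.2 already points to the sensible handling.

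**Conclusion.** No change to the plan follows. The D0 label in SAP 4.4.2.5 is a clerical slip: correct for Group 2, and wrong for Group 1 under the schedule's own use of D0. The intended value for Group 1 is the V02 (M1) sample, which was scheduled at 2 mL and taken before injection. With that value nothing is lost and the effect on the booster-response table is nil. The picture of an arm at 0% and a halved pooled rate requires both that the analyst overlook a visit with no Group 1 serology and that absent values be scored No against SAP 5.3.2, so it is not a fair measure of the problem.

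This rests on two assumptions: that version 1.0 of the protocol gives the same baseline mapping as the amended version, and that SAP 5.3.2 is applied to derived indicators as well as to titres. If the second failed, the exposure would be confined to subjects lacking a sample, in a descriptive table. The primary conclusions would be the same either way.
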